2.2.1 Randomization and drug dispensing irregularities

NA

2.3 ANALYSIS POPULATIONS

All patients enrolled will be included in the safety population. Patients who signed the informed consent but did not participate in any study visit are not considered enrolled in the study.

2.3.1 Efficacy populations

NA

2.3.2 Safety population

The safety population is defined as all patients who enrolled, i.e. signed the informed consent and participated in at least 1 study visit.

2.4 STATISTICAL METHODS

The descriptions of analysis below assume that a sufficient number of patients will be enrolled in the study such that summary statistics of the data will be meaningful to the reviewers. In case of sparse data (less than 5 mothers and/or 5 infants enrolled), the collected data will be presented in patient listings.

2.4.1 Demographics and baseline characteristics

Continuous data will be summarized using the number of available data, mean, standard deviation (SD), median, minimum, and maximum for each treatment group. Categorical and ordinal data will be summarized using the number and percentage of patients in each treatment group.

Parameters described in [Section 2.1.1](#) will be summarized by mother and infant groups using descriptive statistics.

Medical history as collected in the Registry will be presented according to the preprinted case report form history responses.

2.4.2 Prior or concomitant medications

The concomitant medications will be presented for the enrolled population.

Medications will be summarized by treatment group according to the WHO-DD dictionary, considering the first digit of the anatomic category (ATC) class (anatomic category) and the first 3 digits of the ATC class (therapeutic category). All ATC codes corresponding to a medication will be summarized, and patients will be counted once in each ATC category (anatomic or therapeutic) linked to the medication. Consequently, patients may be counted several time for the same medication.

The table for prior medications will be sorted by decreasing frequency of ATC followed by all other therapeutic classes based on the overall incidence across treatment groups. In case of equal frequency regarding ATCs, alphabetical order will be used.

The tables for concomitant medications will be sorted by decreasing frequency of ATC followed by all other therapeutic classes based on the incidence. In case of equal frequency regarding ATCs, alphabetical order will be used.

2.4.3 Extent of investigational medicinal product exposure and compliance

The enrolled mothers will receive Fabrazyme treatment (commercially available) at their currently prescribed dosage regimen as determined by their treating physician. Therefore, the extent of IMP exposure and compliance will not be assessed nor summarized.

2.4.3.1 Extent of investigational medicinal product exposure

The data collected for Fabrazyme infusions received by the mother will be presented in a listing.

2.4.3.2 Compliance

NA

2.4.4 Analyses of efficacy endpoints

2.4.4.1 Analysis of primary efficacy endpoint(s)

NA

2.4.4.2 Analyses of secondary efficacy endpoints

NA

2.4.4.3 Multiplicity issues

NA

2.4.4.4 Additional efficacy analysis(es)

NA

2.4.5 Analyses of safety data

The summary of safety results will be presented by mother and infant groups.

General common rules

All safety analyses will be performed on the safety population as defined in [Section 2.3.2](#). In case of sparse data, the results will be presented in patient listings.

2.4.5.1 Analyses of adverse events

Generalities

All adverse events (AEs) reported from signing of informed consent through completion of the study will be presented.

Adverse event incidence tables will present by SOC and PT, sorted in alphabetical order for each group (mother, infant), the number (n) and percentage (%) of patients experiencing an adverse event. Multiple occurrences of the same event in the same patient will be counted only once in the tables within the study period. The denominator for computation of percentages is the safety population within each group (mother, infant).

Sorting within tables ensures the same presentation for the set of all adverse events within the observation period. For that purpose, the table of all adverse events presented by SOC and PT sorted by the internationally agreed SOC order and decreasing frequency of PTs within SOC will define the presentation order for all other tables unless otherwise specified.

Analysis of all adverse events

The following adverse event summaries will be generated for the safety population.

- Overview of adverse events, summarizing number (%) of patients with any
 - adverse event
 - serious adverse event
 - adverse event leading to death
 - adverse event leading to permanent treatment discontinuation
- All adverse events by primary SOC and PT, showing the number (%) of patients with at least 1 adverse event, sorted by the internationally agreed SOC order and by decreasing incidence of PTs within each SOC. This sorting order will be applied to all other tables, unless otherwise specified
- All adverse events regardless of relationship and related to IMP, by primary SOC and PT, showing the number (%) of patients with at least 1 adverse event
- All adverse events by maximal severity, presented by primary SOC and PT, showing the number (%) of patients with at least 1 adverse event by severity (ie, mild, moderate, or severe)

Analysis of all treatment emergent serious adverse event(s)

- All serious adverse events by primary SOC and PT, showing the number (%) of patients with at least 1 serious adverse event
- All serious adverse events regardless of relationship and related to IMP, by primary SOC and PT, showing the number (%) of patients with at least 1 serious adverse event

- All serious adverse events by maximal severity, presented by primary SOC and PT, showing the number (%) of patients with at least 1 serious adverse event by severity (ie, mild, moderate, or severe)

Analysis of all adverse event(s) leading to treatment discontinuation

- A listing of all adverse events leading to treatment discontinuation will be presented

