#### 9.4.2 Serious Adverse Events

SAEs will be recorded from signed consent through the Month 24 visit (or through the Month 6 visit if only the mother is participating in the study). For patients who discontinue prematurely from the study, SAEs will be reported from signed consent through the last patient study visit. A serious adverse event is defined as any AE that results in any of the following outcomes:

- Death
- Life-threatening experience
- Required or prolonged inpatient hospitalization
- Persistent or significant disability/incapacity
- Congenital anomaly/birth defect
- Important medical events, based upon appropriate medical judgment, that may jeopardize the patient or subject and may require medical or surgical intervention to prevent 1 of the outcomes listed above

Life-threatening experience: any AE that places the patient, in the view of the reporter, at immediate risk of death from the AE as it occurred, ie, does not include an AE that had it occurred in a more severe form might have caused death.

Persistent or significant disability/incapacity: the AE that resulted in a substantial disruption of a person's ability to conduct normal life functions.

Important medical events based upon appropriate medical judgment, that may jeopardize the patient or subject and may require medical or surgical intervention to prevent one of the outcomes listed above: an AE that may not result in death, be life-threatening, or require hospitalization may be considered an SAE when, based upon appropriate medical judgment, it may jeopardize the patient or subject and may require medical or surgical intervention to prevent one of the outcomes listed above.

The Investigator will be asked to assess the severity of the adverse drug/biologic event using the following categories: Mild, Moderate, and Severe. This assessment is subjective and the Investigator should use medical judgment to compare the reported AE to similar types of events observed in clinical practice. Below are listed guidelines for severity assessment:

**Mild:** Symptom(s) barely noticeable to the subject/patient or does not make the subject/patient uncomfortable. The AE does not influence performance or functioning. Prescription drugs are not ordinarily needed for relief of symptom(s).

**Moderate:** Symptom(s) of a sufficient severity to make the subject/patient uncomfortable. Performance of daily activities is influenced. Treatment of symptom(s) may be needed.

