1 OVERVIEW AND INVESTIGATIONAL PLAN

1.1 STUDY DESIGN AND RANDOMIZATION

This is a phase 4, multicenter, multinational study of the potential effects of Fabrazyme on lactation and on the growth, development, and immunologic response of infants born to mothers with Fabry disease who are treated with Fabrazyme during lactation. The mothers will receive Fabrazyme treatment as part of the standard of care of Fabry disease and will be followed through the Fabry Registry.

Pregnant women who received Fabrazyme at any point during their pregnancy can be enrolled in the study. The mothers will receive Fabrazyme treatment (commercially available) at their currently prescribed dosage regimen as determined by their treating physician. If an enrolling woman is not receiving treatment with Fabrazyme at the Baseline visit, she should start treatment with Fabrazyme between the delivery and Month 1 visit.

Approximately 10 mothers and up to 10 infants will be enrolled in this study.

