2.1.4 Safety endpoints

The safety analysis will be based on the reported adverse events (AEs) and other safety information, such as physical examinations, etc.

The following study variables will be summarized as appropriate for the mothers (items marked with * will be collected through the Registry):

- Medical history (including Fabrazyme status during pregnancy)*
- Genotyping*
- Pregnancy outcome*
- IgG antibody status*
- Lactation status
- Plasma and breast milk PK testing
- The level of α GAL, volume, and fat and protein content in breast milk samples
- Frequency of AEs
- Frequency of concomitant medications

The following study variables will be summarized as appropriate for the infants:

- Medical history
- Physical examination
- Gender

- Genotype
- Apgar score at 1 minute and 5 minutes after birth
- Denver II Developmental Screening Test
- IgM antibodies to r-hαGAL – presence, time to development, level of titers present
- IgG antibodies to r-hαGAL – presence, time to development, level of titers present
- Frequency of AEs
- Frequency of concomitant medications

Observation period

The on-study observation period is defined as the time from the signing of the informed consent until the end of the study (defined as last protocol planned patient contact by telephone approximately 28 days after the final study procedures are completed).

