2.1.4.1 Adverse events variables

All AEs ongoing at the time of withdrawal, study termination, or study completion require a follow up at approximately 28 days after discontinuation of study participation. The Investigator will be asked to follow-up on all SAEs that were ongoing at the time of withdrawal, termination or completion until resolution, until both the sponsor and investigator agree follow-up is deemed no longer medically necessary or until the patient is lost to follow-up.

If any new SAEs are identified during the course of this follow-up of ongoing SAEs, additional follow-up of these new SAEs may be performed. The Investigator and sponsor will determine if the follow-up is clinically warranted and relevant to the evaluation of the safety of the trial treatment or until patient is lost to follow up. The investigator must follow patients with AEs until their condition resolves or stabilizes. Certain conditions that are not expected to resolve, such as metastatic cancer, need not be followed indefinitely by the investigator.

All adverse events (including serious adverse events) will be coded to a lower-level term (LLT), preferred term (PT), high-level term (HLT), high-level group term (HLGT), and associated primary system organ class (SOC) using the version of Medical Dictionary for Regulatory Activities (MedDRA) currently in effect at Sanofi at the time of database lock.

All occurrences of adverse events (including serious adverse) from the time of signed informed consent until the end of the study will be recorded.

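### The SAP heads its SAE tables as treatment emergent but counts every SAE from consent, so SAEs in an off-treatment gap carry that label for mothers not on Fabrazyme at Baseline

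*SAP*

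**What the plan says.** SAP 2.4.5.1 groups three SAE tables under one sub-heading ("Analysis of all treatment emergent serious adverse event(s"). The first is specified as "All serious adverse events by primary SOC and PT, showing the number (%) of patients with at least 1 serious adverse event". The other two, by relationship and by maximal severity, are also tables of all serious events. None is limited by onset relative to an infusion.

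The counting window opens at consent throughout:

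- SAP 2.4.5.1: "All adverse events (AEs) reported from signing of informed consent through completion of the study will be presented".
- SAP 2.1.4.1: "All occurrences of adverse events (including serious adverse) from the time of signed informed consent until the end of the study will be recorded".
- Protocol 9.4.2: "SAEs will be recorded from signed consent through the Month 24 visit", or to Month 6 for mother-only participation.

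The SAP defines a single period, in section 2.1.4: "The on-study observation period is defined as the time from the signing of the informed consent until the end of the study", the end being the telephone contact about 28 days after the last procedures. The safety population (SAP 2.3.2) requires consent and one study visit. It does not require an infusion.

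On enrolment, SAP 1.1 admits women treated at any time in the pregnancy and adds: "If an enrolling woman is not receiving treatment with Fabrazyme at the Baseline visit, she should start treatment with Fabrazyme between the delivery and Month" (that is, no later than the first monthly visit). Maternal Baseline lies within 1 month before delivery (SAP 2.1.1), and consent is a Baseline procedure (Protocol 9.1.1.1).

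**The concern.** A table headed treatment emergent tells the reader that the events in it began, or worsened, after treatment started. These tables apply no such condition. For a mother off Fabrazyme at Baseline, the last weeks of pregnancy, the delivery and the first weeks postpartum can all fall after consent and before her first infusion after Baseline.

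The following record is hypothetical. A mother off Fabrazyme consents 3 weeks before delivery, has a delivery complication that prolongs her hospital stay (serious under Protocol 9.4.2), and has her first infusion after delivery 3 weeks later. She received no Fabrazyme between consent and the event, yet her SAE enters a table under the treatment-emergent heading.

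At stake is how the maternal SAE figures are read in a small study with no reference treatment. Exposure is not summarised (SAP 2.4.3) and infusions appear only in a listing (SAP 2.4.3.1), so the tables alone cannot show which events preceded treatment.

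**Working it through.** The plan gives no figure to reproduce: the study is descriptive, without a sample size calculation. The check is mainly of the text, followed by calendar arithmetic.

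**1. Label against content.** The heading requires onset relative to treatment. The tables, the AE counting rule, the observation period and the safety population all run from consent. No other passage supplies a restriction. Protocol 9.4.1 says that signs present before study medication are not AEs after treatment unless they recur or worsen, but the same section counts any untoward sign from consent onward. It therefore does not narrow the tables.

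**2. Longest off-treatment gap inside the counted window.** Inputs: consent no earlier than 1 month before delivery; first infusion no later than the Month 1 visit; visit window ±7 days (Protocol Table 1). One month is taken as 365.25/12 = 30.44 days.

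- Nominal: 30.44 + 30.44 = 60.9 days.
- With the Month 1 visit 7 days late: 60.9 + 7 = 67.9 days.

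**3. Share of a mother's observation period**, from consent 1 month before delivery to the 28-day call:

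| Schedule | Total days | Gap 60.9 days | Gap 67.9 days |
|---|---|---|---|
| To Month 6 | 7 × 30.44 + 28 = 241.1 | 25% | 28% |
| To Month 24 | 25 × 30.44 + 28 = 788.9 | 8% | 9% |

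**4. Weight of one mother.** The denominator is the maternal safety population, about 10. Patients are counted once, so a mother whose only SAE falls in the gap adds 1/10 = 10 percentage points compared with a table limited to onset on treatment. A mother who also has a later SAE on treatment adds nothing to the overall percentage.

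**5. Illustration on assumed inputs.** The documents give neither the number of mothers off Fabrazyme at Baseline (k) nor the probability of an SAE in the gap (q). Take k = 1 to 5 of 10 and q = 5% to 30%.

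- Chance that at least one such mother is in the table, 1 − (1 − q)^k: from 1 − 0.95 = 5% (k = 1, q = 5%) to 1 − 0.70^5 = 83% (k = 5, q = 30%).
- Expected share of all mothers with a gap SAE, k × q/10: from 0.5 points (1 × 0.05/10) to 15 points (5 × 0.30/10). By step 4, this is an upper limit on the expected shift in the reported percentage.

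**The case against.** The strongest reply is that this is a labelling slip. The term occurs once, in a sub-heading. The tables beneath it are called all-SAE tables, and the window from consent is stated openly and consistently. Other template wording that does not fit this study survives in the SAP, such as references to treatment groups. The heading also spans the infant tables, although infants receive no infusion. Deleting two words would remove the contradiction without changing any count. This stands, and it sets the minimum fix. It does not tell a reader of the maternal tables which SAEs fell in the gap.

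The tables by relationship to the product give partial protection. It is only partial, because SAP 2.5.3 counts an event with a missing relationship assessment as related.

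A reader might infer more than the documents support:

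- *That all maternal AE tables are mislabelled.* They are presented as all adverse events and match their stated window. Splitting them by period is an improvement, not a correction.
- *That the gap precedes any exposure.* Women treated earlier in the same pregnancy are eligible, so it may be an interruption.
- *That the reported SAE percentage is inflated by a large known amount.* Assuming a hazard of 0.02–0.05 per month and a 5–20% delivery-event probability gives an excess of about 8 to 21 points, but only among mothers off treatment at Baseline and followed to Month 6. The SAP reports no such subgroup, and the inputs have no source in the documents. If 1 to 3 of 10 mothers were off treatment, the group shift on those inputs would be about 0.8 (0.1 × 7.8) to 6 points (0.3 × 20.6).
- *That the label explains any mixing of childbirth with treatment.* For mothers already on Fabrazyme at Baseline, delivery events occur on treatment under any reasonable definition.

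**Conclusion.** The point holds as a contradiction between one heading and its tables, together with a missing definition. Collecting events from consent is sound. What fails is the treatment-emergent label for SAEs that a mother off Fabrazyme at Baseline has before her first infusion after Baseline, a gap of up to about 61 days, or about 68 with the visit window.

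The size is 10 percentage points for each mother whose only SAE falls in the gap, assuming about 10 mothers in the denominator. The total effect cannot be stated because the number of such mothers is not given. It is zero if none enrol. With fewer than 5 mothers and/or 5 infants enrolled, SAP 2.4 replaces tables with listings, and the tabulated percentage does not arise. The gap lengths assume consent within the month before delivery and a first infusion by the Month 1 visit.

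**What to change.** 1. Remove the term treatment emergent from the heading in SAP 2.4.5.1 and keep these tables as all on-study SAEs, for mothers and infants. The term has no meaning for infants.
2. For mothers, add one flag that splits AEs and SAEs by onset: before, or on or after, the first Fabrazyme infusion after consent. Count mothers already on Fabrazyme at Baseline as on treatment from consent, so that columns and definition agree. A split of all mothers at the first postpartum infusion would put events of already-treated mothers in the wrong column.
3. Derive the flag from the infusion data (SAP 2.4.3.1: "The data collected for Fabrazyme infusions received by the mother will be presented in a listing"). First confirm that the date of the first infusion after Baseline is captured: that section does not name the fields, and Protocol Tables 1 to 3 show no item for recording infusions.
4. State that events whose onset cannot be placed go in the on-treatment column. SAP 2.5.3 does not impute onset dates, so a rule is needed.

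The cost is SAP wording and one derived variable, provided the infusion date is held. The downside is thinner cells in a table of about 10 mothers; the combined table remains. Treatment and visits are unaffected.

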2.4.5.2 Deaths

A listing of adverse events leading to death (death as an outcome on the adverse event case report form page as reported by the Investigator) will be presented.

2.4.5.3 Analyses of laboratory variables

NA

2.4.5.4 Analyses of vital sign variables

NA

2.4.5.5 Analyses of electrocardiogram variables

NA

2.4.5.6 Analyses of other safety endpoints

2.4.6 Analyses of pharmacokinetic and pharmacodynamic variables

Descriptive statistics of pharmacokinetic (PK) parameters by visit and by mother and infant groups will be provided. However, in case of sparse data, a by patient listing will be provided.

2.5 DATA HANDLING CONVENTIONS

2.5.1 General conventions

None.

2.5.2 Data handling conventions for secondary efficacy variables

NA

2.5.3 Missing data

For categorical variables, patients with missing data are not included in calculations of

percentages unless otherwise specified. When relevant, the number of patients with missing data is presented.

Handling of medication missing/partial dates

No imputation of medication start/end dates or times will be performed. If a medication date or time is missing or partially missing and it cannot be determined whether it was taken prior or concomitantly, it will be considered a concomitant medication.

Handling of adverse events with missing or partial date/time of onset

Missing or partial adverse event onset dates and times will not be imputed. No imputation of adverse event end dates/times will be performed. No imputation is planned for date/time of adverse event resolution.

Handling of missing assessment of relationship of adverse events to investigational medicinal product

If the assessment of the relationship to IMP is missing, then the relationship to IMP has to be assumed and the adverse event considered as such in the frequency tables of possibly related adverse events, but no imputation should be done at the data level. No imputation of relationship will be presented in the listings.

Handling of missing severity of adverse events

If the severity is missing for 1 of the occurrences of an adverse event, the maximal severity on the remaining occurrences will be considered. If the severity is missing for all the occurrences, a “missing” category will be added in the summary table.

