## 6 INVESTIGATIONAL PLAN

### 6.1 STUDY DESIGN

This is a phase 4, multicenter, multinational study of the effects of Fabrazyme on lactation and on the growth, development, and immunologic response of infants born to mothers with Fabry disease who are treated with Fabrazyme during lactation. There are 3 participation scenarios: mother/infant full participation, mother full participation/infant development only, and mother full participation/infant no participation (see [Section 9.1](#)).

Whether or not the mother continues to lactate will be assessed at each visit. Breast milk will be collected at Months 1, 3, and 6 immediately prior to Fabrazyme infusion, just after the end of the infusion, and 2 hours after the end of the infusion. Breast milk samples will be analyzed for volume, presence of  $\alpha$ GAL activity, total fat content, and total protein concentration. Blood samples from the mother will be drawn for pharmacokinetic (PK) analysis prior to each breast milk collection. If infant genotyping is performed on the umbilical blood cord sample collected at Baseline visit, a buccal cell sample will be obtained from the mother to rule out contamination of the cord blood sample with maternal DNA.

If the parent(s)/legal guardian(s) consent to infant participation, the infant's growth and development will be assessed. The infant may also be tested for the formation or continued presence of serum IgG and IgM antibodies to r-h $\alpha$ GAL and for genotype.

For the purposes of this study, the mother and the infant will each be considered a study patient. The mother must be enrolled in the Fabry Registry and will be followed using the Fabry Registry assessment schedule and CRFs as well as this study's CRF. During this study, infants will be evaluated, ie, the infant may be tested for IgG and IgM antibodies to r-h $\alpha$ GAL at birth and Months 2, 6, and 12 and will be tested developmentally at each visit for 24 months, or until the parent(s)/legal guardian(s) withdraws consent and discontinues the infant's study participation, the infant is discontinued from the study by the Investigator (see [Section 7.3.1](#)), or the study is terminated (see [Section 7.3.2](#)).

If the mother is no longer lactating, the mother will discontinue this study but continue to be followed in the Fabry Registry. The infant will be followed for development only for the remainder of this 24 month study.

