### **9.4.6 Status of Lactation/Receiving Breast Milk**

Whether or not the mother is lactating will be recorded at each visit on the mother's CRF.

If the infant is participating in this study, whether or not the infant is receiving breast milk will be recorded at each visit on the infant's CRF.

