## **11 STATISTICAL METHODS AND PLANNED ANALYSES**

### **11.1 GENERAL CONSIDERATIONS**

Genzyme will be responsible for data entry and editing, reviewing all the information in the CRFs, statistical analysis, and generation of the clinical report.

Clinical data will be double-entered and validated in an Oracle database using Clintrial 4.5.

The Genzyme Biomedical Data and Informatics will perform the statistical analysis of the data derived from this study. The analysis will be performed using the SAS® statistical software system. (9)(10) The status of this study will be summarized annually as part of the Fabry Registry Program Annual Report.

Any missing or invalid data will not be replaced or imputed.

Data collected in this study will be reported using summary tables, graphs, figures, and/or patient data listings.

No hypothesis testing will be performed.

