1.2 OBJECTIVES

1.2.1 Primary objectives

The primary objectives of this study are:

1. To determine whether α GAL activity is present in the breast milk of mothers with Fabry disease who are being treated with Fabrazyme during lactation.
2. To measure breast milk production and composition (volume, protein and fat content) in women with Fabry disease who receive Fabrazyme during lactation.
3. To determine whether Fabrazyme affects the growth, development, and immunologic response of infants born to mothers with Fabry disease who receive Fabrazyme during lactation.

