1.3 DETERMINATION OF SAMPLE SIZE

No formal statistical sample size calculations were performed for this study. The sample size of approximately 10 mothers and up to 10 infants is based upon 1) the availability of mothers to study lactation in this rare disease and 2) the availability of infants whose parents or legal guardians consent to their participation in this study.

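### Mothers who stop lactating leave the study and drop out of the percentages, so a post-baseline lactation rate would overstate the share of enrolled mothers still lactating

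*SAP*

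**What the plan says.** Protocol 6.1 sets the exit rule: "If the mother is no longer lactating, the mother will discontinue this study but continue to be followed in the Fabry Registry". SAP 1.4 repeats it. Protocol 6.2.2 adds a second route out, for a mother who is no longer receiving Fabrazyme.

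Protocol 9.4.6 states: "Whether or not the mother is lactating will be recorded at each visit on the mother's CRF". Tables 1 and 2 schedule this to Month 24; Table 3 (mother only) stops at Month 6. Protocol 11.8 and SAP 2.1.4 both list lactation status among the maternal variables to be summarised.

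On missing values, SAP 2.5.3 says: "For categorical variables, patients with missing data are not included in calculations of" percentages, unless something else is specified, with the number missing shown where relevant. Protocol 11.1 adds: "Any missing or invalid data will not be replaced or imputed". Nothing else is specified for lactation status. SAP 2.4.5.6 (other safety endpoints) has a heading and no text, SAP 2.5.1 gives no general conventions, and the enrolled-patient denominator in SAP 2.2 is stated for disposition only.

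For milk, note d of Tables 1 to 3 requires that the mother be lactating and on Fabrazyme when sampled. SAP 1.2.1 makes this a primary objective: "To measure breast milk production and composition (volume, protein and fat content) in women with Fabry disease who receive Fabrazyme during lactation".

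**The concern.** The outcome being summarised is itself what removes a mother from the study. Once she has left, her later visits are blank, the percentage rule takes her out of both numerator and denominator, and the ban on replacement prevents her return as a 'No'. Yet her status is not unknown: Protocol 7.3.1 lists end of lactation among the reasons for removal and has the investigator record the reason for discontinuation on the CRF.

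The resulting figure is a continuation rate among mothers who were lactating when last seen. It answers a different question from how many enrolled mothers are still lactating. The study is about effects on lactation and has no reference group, so a high percentage at later visits could easily be read as evidence that lactation was maintained. Mean milk volume at Months 3 and 6 raises a related issue, because it describes only those mothers still able to give a sample.

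**Working it through.** **Inputs**
- N = 10 mothers. SAP 1.1: "Approximately 10 mothers and up to 10 infants will be enrolled in this study".
- There is no planned figure to reproduce. SAP 1.3: "No formal statistical sample size calculations were performed for this study"; Protocol 11.1: "No hypothesis testing will be performed".
- P = mothers who stopped lactating and left before the visit; s = mothers first recorded as not lactating at the visit. Neither is in the documents, so a range is shown. Steps 1 to 3 assume that every exit is for end of lactation, all ten mothers have the visit on their schedule, and none misses it.

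**Step 1: formula.** Under the default rules the percentage lactating is (N − P − s)/(N − P). With known stops kept as 'No' it is (N − P − s)/N. The difference is P(N − P − s)/[N(N − P)], which is positive whenever P > 0 and at least one mother still lactates. It is zero at the visit where the first 'No' is recorded.

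**Step 2: one visit, N = 10**

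| P | s | Default rules | All enrolled | Excess (points) |
|---|---|---|---|---|
| 1 | 0 | 9/9 = 100% | 9/10 = 90% | 10 |
| 1 | 1 | 8/9 = 88.9% | 8/10 = 80% | 8.9 |
| 3 | 0 | 7/7 = 100% | 7/10 = 70% | 30 |
| 3 | 1 | 6/7 = 85.7% | 6/10 = 60% | 25.7 |
| 5 | 0 | 5/5 = 100% | 5/10 = 50% | 50 |
| 5 | 1 | 4/5 = 80% | 4/10 = 40% | 40 |

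**Step 3: three assumed stopping patterns** (new stops at Months 1, 2, 3, 6, 12, 18, 24)
- Slower (0, 0, 1, 1, 2, 2, 1): Month 6, 8/9 = 88.9% against 80%; Month 24, 3/4 = 75% against 30%.
- Middle (0, 1, 1, 2, 3, 2, 1): Month 3, 8/9 = 88.9% against 80%; Month 6, 6/8 = 75% against 60%; Month 12, 3/6 = 50% against 30%.
- Faster (2, 1, 2, 2, 2, 1, 0): Month 1, 80% on both; Month 3, 5/7 = 71.4% against 50%; Month 6, 3/5 = 60% against 30%.

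**Step 4: where the 'No' is recorded.** Lactation status is also recorded at early withdrawal (Protocol 9.1.1.8, 9.1.2.8, 9.1.3.4), but the SAP does not say under which visit that record is tabulated. SAP 2.5.5 keeps unscheduled measurements out of by-visit summaries. If every 'No' fell in such a record and were treated as unscheduled, each visit with any mother left would read 100%.

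**Step 5: the other exit route.** Suppose three mothers stop Fabrazyme after Month 3 while still lactating, continue to lactate, and one other mother stops lactating at Month 6. The default rules give 6/7 = 85.7%; the proportion of all ten still lactating is 9/10 = 90%. Here the figure is too low.

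**Step 6: milk volume.** Assume ten volumes from 20 to 110 mL in steps of 10, with mean 650/10 = 65 mL. If the three lowest producers (20, 30 and 40 mL) stop and nobody else changes, the mean becomes 560/7 = 80 mL. That is an apparent rise of 15 mL with no change in any remaining mother. The volumes and the order of stopping are invented to show the mechanism.

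**The case against.** The strongest reply is that no by-visit lactation percentage is actually specified. SAP 2.1.4 says only that variables are summarised as appropriate, and SAP 2.1.1 describes lactation status as two yes/no questions under baseline characteristics. That stands: the percentage is what the default rules would produce, not a table the SAP describes. But the variable is collected at every visit and listed for summary, and those rules are the only ones given.

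There are also safeguards: the number missing is shown where relevant, attendance and discontinuations are tabulated (Protocol 11.5), exit reasons are recorded, participating infants' breast-milk status continues to be recorded, and listings replace tables if fewer than 5 are enrolled (SAP 2.4). With about 10 mothers an attentive reader could reconstruct much of the picture. None of this corrects the percentage itself.

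Three stronger readings are tempting, and the documents do not support them. A reader might infer that every post-baseline visit is overstated; visits up to and including the one where the first stop is recorded are not. A reader might infer that the error always favours an impression of no effect; Step 5 shows the opposite is possible, and with no comparator or test that direction has no defined reference. A reader might infer that milk volume is biased upward because poor producers leave; nothing says mothers stop for lack of supply. The milk restriction comes from the sampling condition and exit rules, not from SAP 2.5.3, and the objective itself concerns women treated during lactation. Means at one visit and pre- to post-infusion comparisons within a visit are valid as conditional descriptions; only comparisons of means across months are exposed.

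**Conclusion.** The point holds for any post-baseline percentage of mothers lactating that is produced under the default rules, at visits after the first mother has stopped and left, while at least one still lactates. With 10 mothers the excess runs from about 9 to 50 points over the one-visit cases shown. These sizes depend on the assumed stops, on end of lactation being the only exit reason and, beyond Month 6, on all ten mothers having participating infants. For milk volume the supported conclusion is narrower: the mean is conditional on still lactating and still treated, so a change in the mean between Months 1, 3 and 6 may reflect who remains. The study is descriptive, so no test or error rate is affected. It should be corrected because the true status of these mothers is known and the default figure misdescribes a central subject of the study.

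**What to change.** Use the exception that SAP 2.5.3 already allows. The exit rule need not change.

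- Count a mother whose recorded exit reason is end of lactation as 'not lactating' at all her later scheduled visits. The denominator is all enrolled mothers whose schedule includes the visit; the mother-only schedule has no Month 2 visit and ends at Month 6.
- Show exits for other reasons, including stopping Fabrazyme, as a separate category.
- State that this uses the recorded exit reason and is not imputation under Protocol 11.1.
- List or summarise when lactation ended, using status recorded at early withdrawal, and say how those records enter the by-visit tables.
- Label milk volume as conditional on lactating and receiving Fabrazyme, with n per visit. Base any statement about change over time on mothers sampled at each of the visits compared.

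The cost is a short SAP addition and slightly more programming. The exit reason is already collected, so the correction to the percentage needs no new CRF field. The reported lactation percentage will usually look less favourable.
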